## 909 **Interim Analysis**

910

911 We plan to perform interim analysis on the primary safety endpoint every 6 months. The  
912 trial will be stopped if there is evidence beyond a reasonable doubt of a difference in the rate of  
913 death (two-sided alpha level, <0.01) between the treatment groups. In addition, the trial will be  
914 stopped if the rate of severe hypoglycemic events (BG <40 mg/dl) in either group is > 40%.

915 **Explorative Statistical Analysis for Pharmacogenetics and Biomarkers**

916 N/A

917 **DATA HANDLING AND RECORD KEEPING:**

918 Data collection records with personal identifiers will be stored in locked file cabinets.  
919 Sponsor site expects data to be entered in REDCap within 10 days of phone call or outpatient  
920 visit. The study coordinators will enter data from each visit into data collection paper forms and  
921 into an electronic database (REDCap) that meets HIPPA and confidentiality regulations,  
922 provided by the Emory Research Information Technology Department. Baseline data will include  
923 demographics/history form (subject's gender, date of birth, ethnicity, history of diabetes, and  
924 treatment of diabetes and comorbid conditions, body weight, BMI. During follow-up visits, data  
925 from SMBG, laboratory and/or CGM will be also collected. Data on adverse events will also be  
926 collected and enter into the database. Presentation of the study results at regional or scientific  
927 meetings or in publications will not identify subjects. Access to research and confidential  
928 records will be limited to clinical investigators, research coordinators, and the IRB at Emory  
929 University.

930

931 **ETHICS:**

932 **Informed Consent.**

933 After identification of eligible patients these individuals will be provided basic information  
934 regarding the study and, if interested, a member of the research staff using inclusion/exclusion  
935 criteria delineated elsewhere in the protocol will enroll patients. Informed consent will be  
936 obtained before any trial related procedures including screening procedures. The consent form,  
937 potential risks and benefits, and the rights of research participants will be explained to the  
938 participant by the investigators or research coordinator. Individuals will be asked if they have  
939 questions, and a member of the research staff will answer questions. The principal investigator

940 will also be available at all times to answer questions that participants may have during the  
941 consent procedure or during the time a participant is enrolled in the study. The consent form  
942 will be completed in accordance with the IRB guidelines of Emory University. A signed copy of  
943 the consent form will be provided to the participant and a copy will be placed in the file that is  
944 maintained for each participant in the study office.

945 Informed consent will follow the procedure of Emory University Institutional Review  
946 Board. Every potential participant will be informed in writing and verbally with the important and  
947 key points of the study. One of the investigators or research coordinators will obtain an  
948 informed consent prior to inclusion of a patient into the study.

949 The study will be conducted in accordance with the Declaration of Helsinki and will be  
950 conducted in accordance with the ICH GCP guidelines. The sponsor-investigator will comply  
951 with all applicable regulatory and legal requirements, ICH GCP guidelines and the Declaration  
952 of Helsinki in obtaining and documenting the informed consent.

953

954 **STUDY SCHEDULE:**

955 The study will be conducted at two sites: at 1) Emory University Hospital Midtown and  
956 Grady Memorial Hospital in Atlanta, GA; and at 2) TBA. An additional site will be considered if  
957 funds are available.

958 Based on our prior trials experience, we anticipate 3-4 potential candidates per week,  
959 including the collaborating institutions, for a total recruitment period of approximately 12  
960 months. Since the study requires a 6-month follow up period, we anticipate a study length of  
961 18-24 months.

First subject in	2019 January
Screening	~300
Randomized	150
Last subject recruited	2020 June/July
Last subject in (completed)	2021 Nov/Dec
Data analysis	2021 DEC
Submission to congress or journal	ADA 2021, Major journal and/or Diabetes Care 2021

962

963 **Study DRUGS and materials:**

964 **Study medication(s) / devices(s)**

965 • Group 1: IDegLira pens will be supplied by the sponsor and given free of charge to the study  
966 subjects. IDegLira is a FRC agent, including basal insulin degludec and GLP-1 agonist

967 liraglutide. The starting dose of IDegLira is at 16 dose steps (degludec 16 units/liraglutide  
968 0.6 mg). The maximum allowed dose of IDegLira 50 dose steps provide 50 U of  
969 degludec and 1.8mg of liraglutide.

970 • Group 2: Degludec U-100 and Aspart U-100 insulin pens will be supplied by the  
971 sponsor and given free of charge to the study subjects.

972 • We will use a professional CGM device. The investigator will keep the sensor readers, and  
973 will store the transmitters after the completion of each sensor study for up to 5 years- as  
974 part of the study information.

975

### 976 **Packaging and Labelling of Study Medication(s)**

977 Trial products will be packed and labelled by Emory and Grady Investigational Drug Service.  
978 Labelling will be in accordance with local law and study requirements.

979

### 980 **Storage and Drug Accountability of Study Medication(s)**

981 Emory and Grady Investigational Drug Service, is a full-service research pharmacy with  
982 all required conditions for proper storage and dispensing of study medications. The investigator  
983 will ensure the availability of proper storage conditions and record and evaluate the temperature.  
984 There will be no trial medication(s) dispensed to any person not enrolled in the study. Any  
985 unused medication(s) will be stored separately from used trial medication(s). Subject  
986 compliance will be assessed by asking subjects to return all unused, partly used and unused  
987 cartridges and vials of liraglutide and degludec insulin at each visit. Subjects will be instructed to  
988 return all used, partially used or unused study products before each dispensing visit. Subjects  
989 will be encouraged at every visit to adhere to the study medications and follow-up schedule. Any  
990 partially used or unused study medications will be destroyed accordingly to local procedures.  
991 After study completion, any surplus of study medications or supplies will be disposed as per local  
992 regulations.

993

### 994 **Auxiliary Supply**

995 Investigator will provide the following supplies:

996 • Needles for insulin pens, IDegLira, Degludec and Aspart pens

### 997 **Randomization and Blinding**

998 This is an open label randomized controlled trial. Patients will be randomized  
999 consecutively using a computer-generated randomization table provided by [name],  
1000 Professor of Statistics at the Emory School of Public Health. Patient will be randomized based  
1001 on HbA1c (HbA1c <10 or ≥10). The randomization table will be mailed to each institution where

1002 a member of the research team will be in charge of the randomization process and group  
1003 assignment.

1004 **Breaking of Blinded Codes**

1005 N/A

1006

1007

1008 **CONCOMITANT ILLNESSES AND MEDICATIONS:**

1009 **Definitions:**

1010 Concomitant illness: any illness that is present at the start of the trial (*i.e. at the first visit*).

1011 Concomitant medication: any medication other than the trial product(s) that is taken during the  
1012 trial, including the screening and run-in periods.

1013 Details of all concomitant illnesses and medication must be recorded at trial entry (*i.e. at the first*  
1014 *visit*). Any changes in concomitant medication must be recorded at each visit. If the change  
1015 influences the subject's eligibility to continue in the trial, the sponsor must be informed.

1016 The information collected for each concomitant medication includes, at a minimum, start date,  
1017 stop date or continuing, and indication.

1018 For each concomitant illness, date of onset, date of resolution or continuing, at a minimum,  
1019 should be recorded.

1020

1021 **ADVERSE EVENTS:**

1022 The investigator will be responsible for reporting of all adverse events including serious  
1023 adverse events (SAE), serious adverse drug reactions (SADRs) to the competent authority and  
1024 independent IRB boards based upon federal regulations and local/IRB policies. The investigator  
1025 will report to the sponsor all S A R D s at the same time it's reported to the IRB or within 15  
1026 days of the investigator becoming aware.

1027 The investigators will collect the following information at minimum for each of these events:

1028 1. Study name

1030 2. Patient identification (e.g. initials, sex, age)

1031 3. Diagnosis

1032 4. Drug

1033 5. Reporter identification (e.g. Name, or initials)

1034 1035 Also 6) Causality, and 7) Outcome might be reported, but this is not mandatory.

1036

1037

1038

1039

1040 **Definitions**

1041 **Adverse Event (AE):**

1042 An AE is any undesirable medical event occurring to a subject in a clinical trial, whether  
1043 or not related to the trial product(s). This includes events reported from the first trial related  
1044 activity after the subject has signed the informed consent and until post treatment follow-up  
1045 period as defined in the protocol.

1046 **Adverse Reaction (AR)**

1047 An AR is an adverse event for which the causal relationship between the product and the  
1048 adverse event is suspected.

1049 The following should not be recorded as AEs, if recorded as medical history/concomitant illness  
1050 on the CRF at screening:

- 1051 • Pre-planned procedure, unless the condition for which the procedure was planned has  
1052 worsened from the first trial related activity after the subject has signed the informed consent
- 1053 • Pre-existing conditions found as a result of screening procedures

1054  
1055  
1056 **Clinical Laboratory Adverse Event:**

1057 A clinical laboratory AE is any clinical laboratory abnormality regarded as clinically  
1058 significant i.e. an abnormality that suggests a disease and/or organ toxicity and is of a severity,  
1059 which requires active management, (i.e. change of dose, discontinuation of trial product, more  
1060 frequent follow-up or diagnostic investigation).

1061

1062 **Serious Adverse Event (SAE):**

1063 A serious AE is an experience that at any dose results in any of the following:

- 1064 • Death
- 1065 • A life-threatening\* experience
- 1066 • In-patient hospitalization or prolongation of existing hospitalization
- 1067 • A persistent or significant disability/incapacity
- 1068 • A congenital anomaly/birth defect
- 1069 • Important medical events that may not result in death, be life-threatening\*, or require  
1070 hospitalization may be considered an SAE when, based upon appropriate medical judgement,  
1071 they may jeopardize the subject and may require medical or surgical intervention to prevent one  
1072 of the outcomes listed in this definition
- 1073 • Suspicion of transmission of infectious agents

1074 \*The term life-threatening in the definition of SAE refers to an event in which the subject was at  
1075 risk of death at the time of the event. It does not refer to an event which hypothetically might  
1076 have caused death if it was more severe.

1077

1078 **Serious Adverse Drug Reaction (SADR):**

1079 An adverse drug reaction is an adverse event (AE) for which a causal relationship to the  
1080 trial product is at least possible i.e. causal relationship is conceivable and cannot be dismissed.  
1081 Serious adverse reaction (SAR): Adverse event which fulfils both the criteria for a Serious  
1082 Adverse Event and the criteria for an Adverse Reaction.

1083

1084

1085

1086 **Suspected Unexpected Serious Adverse Reaction (SUSAR):**

1087 An SAE which is unexpected and regarded as possibly or probably related to the  
1088 trial/study product by the investigator.

1089

1090 **Medical Events of Special Interest (MESI):** A MESI is (1) a medication error (e.g. wrong drug  
1091 administration or wrong route of administration) or (2) a suspected transmission of an infectious  
1092 agent via the product

1093

1094 **Non-Serious Adverse Event:**

1095 A non-serious AE is any AE which does not fulfil the definition of an SAE.

1096

1097

1098 **Severity Assessment Definitions:**

1099 • Mild: Transient symptoms, no interference with the subject's daily activities

1100 • Moderate: Marked symptoms, moderate interference with the subject's daily activities

1101 • Severe: Considerable interference with the subject's daily activities, unacceptable

1102

1103

1104 **Relationship to study medication Assessment Definitions:**

1105 • Probable: Good reasons and sufficient documentation to assume a causal relationship

1106 • Possible: A causal relationship is conceivable and cannot be dismissed

1107 • Unlikely: The event is most likely related to an etiology other than the trial product

1108

1109

1110 **The US PI, will be used to evaluate all unexpected events and adverse reactions.**

1111

1112

1113 **Outcome Categories and Definitions:**

- 1114 • Recovered: Fully recovered or by medical or surgical treatment the condition has returned to  
1115 the level observed at the first trial related activity after the subject signed the informed consent
- 1116 • Recovering: The condition is improving and the subject is expected to recover from the event.  
1117 This term should only be used when the subject has completed the trial
- 1118 • Recovered with sequelae: As a result of the AE, the subject suffered persistent and  
1119 significant disability/incapacity (e.g. became blind, deaf, paralyzed). Any AE recovered with  
1120 sequelae should be rated as an SAE
- 1121 • Not recovered
- 1122 • Fatal
- 1123 • Unknown

1124

1125 **Collection, Recording and Reporting of Adverse Events**

1126 All events meeting the definition of an adverse event must be collected and reported  
1127 from the first trial related activity after the subject has signed the informed consent and until the  
1128 end of the posttreatment follow-up period as stated in the protocol.

1129

1130 **Follow-up of Adverse Events**

1131 During and following a subject's participation in a clinical trial, the investigator will provide  
1132 adequate medical care to the study subject for any study-related adverse events, including  
1133 clinically significant laboratory values related to the study, regardless of their insurance status.

1134 All adverse events classified as serious or severe or possibly/probably related to the trial  
1135 product must be followed until the subject has recovered and all queries have been resolved.

1136 For cases of chronic conditions follow-up until the outcome category is "recovered" is not  
1137 required, as these cases can be closed with an outcome of "recovering" or "not recovered".

1138 All other adverse events must be followed until the outcome of the event is "recovering" (for  
1139 chronic conditions), or "recovered" or until the end of the post-treatment follow-up stated in the  
1140 protocol, whichever comes first, and until all queries related to these AEs have been resolved.

1141

1142 **Pregnancy**

1143 Subjects will be instructed to notify the sponsor-investigator immediately if they become  
1144 pregnant.

1145 The investigator will report to Novo Nordisk any pregnancy occurring during the trial  
1146 period. Reporting of pregnancy by investigator should occur within the same timelines described

1147 above for reporting of Adverse Events.

1148           Pregnancy complications should be recorded as adverse event(s). If the infant has a  
1149 congenital anomaly/birth defect this must be reported and followed up as a serious adverse  
1150 event.

1151

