**Assessments for Efficacy**

791 The primary outcome of efficacy will be determined by change of HbA1c from baseline  
792 after 26 weeks of treatment. HbA1c will be measured by the clinical laboratory of  
793 Grady Memorial Hospital and Emory University, a NGSP-certified laboratory. Subjects will  
794 complete an 8-point SMBG for at least 1 day before the CGM visits. We will also compare the  
795 time in target range (70-180) as detected by CGM, allowing us to assess glycemic control for > 7  
796 days with frequent testing (CGM and POC BG). We will compare the rate of "responders",  
797 defined as patients HbA1c  
798 <7.0% and no hypoglycemia at week 26.

799  
800

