### 866 **Subject Compliance**

867 Subject compliance will be assessed by monitoring of drug accountability. Subjects will be  
868 encouraged at every visit to adhere to the study medications and follow-up schedule. Unused  
869 trial medications will be compared with dispensed amount at each corresponding visit. If  
870 discrepancies are noted, the subject will be asked.

871  
872 **STATISTICAL CONSIDERATIONS:**  
873 **Sample Size Calculation**  
874       The primary outcome is the change in HbA1c from baseline after 26-weeks of treatment.  
875       The primary hypothesis is that HbA1c change is similar between the IDegLira group and the  
876       basal-bolus group. Given the data reported for the DUAL V study, we assume the HbA1c  
877       change from baseline has a standard deviation bounded above by 0.85 (%). We assume the  
878       margin of equivalence is 0.4 (%) and the true mean difference in the primary outcome is 0 (%).  
879       Given 57 subjects per study group, based on a one-sided, two-sample t-tests, we would achieve  
880       80% power to detect non-inferiority, with alpha (type-1 error) set as 0.05. Accounting for 20%  
881       attrition rate of 20%, we need to recruit 75 subjects per group (150 in total).  
882  
883 **Statistical Methods**  
884       This is a randomized, open-label study. We will first compare the primary outcome (i. e.  
885       change in HbA1c from baseline to after 26 weeks of treatment) between the two study groups  
886       using nonparametric and parametric two-sample tests, such as Wilcoxon tests and t-tests. A  
887       logarithm transformation may be employed to make the data better conform to the normality  
888       assumption. We will apply standard variable selection and model checking procedures to decide  
889       the final model.  
890       Secondary outcomes include various measurements (related to glycemic control, quality  
891       of life, adverse effects, and etc.) collected at a single or multiple time points. For continuous  
892       outcomes measured a single time point (i.e. non-longitudinal outcome), we shall analyze them  
893       following the same strategy designed for the primary outcome. For discrete non-longitudinal  
894       outcome, we will use Chi-square (or Fisher's Exact) tests to compare them between the two  
895       study groups. This will be followed by logistic regression or Poisson (or Negative Binomial)  

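### The deciding analysis of HbA1c change is left to variable selection, so neither institution nor the declared HbA1c stratum is fixed in the primary model

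*Combined protocol and SAP*

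**What the plan says.** Randomization and Blinding describes a computer-generated table. Patients are randomised "on HbA1c (HbA1c <10 or ≥10). The randomization table will be mailed to each institution where" a member of the research team handles randomisation and assignment. HbA1c below 10 versus 10 or above is the only factor named. Separate lists or blocks per institution are not described.

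Study Schedule states: "The study will be conducted at two sites: at 1) Emory University Hospital Midtown and" Grady together form the first site. The second is still to be announced.

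Sample Size Calculation defines the outcome: "The primary outcome is the change in HbA1c from baseline after 26-weeks of treatment". It assumes that the "change from baseline has a standard deviation bounded above by 0.85 (%). We assume the" "margin of equivalence is 0.4 (%) and the true mean difference in the primary outcome is 0", and sizes the trial on an unadjusted test: "Given 57 subjects per study group, based on a one-sided, two-sample t-tests, we would achieve" 80% power at one-sided alpha 0.05.

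Statistical Methods first compares the arms "using nonparametric and parametric two-sample tests, such as Wilcoxon tests and t-tests. A" log transformation is optional. Variable selection and model checking then determine a final model. No covariate is named, whether institution, stratum or baseline HbA1c. The section does not say which of these analyses decides non-inferiority, and it defines no confidence interval for that decision.

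**The concern.** Each institution runs allocation locally. In this open-label, treat-to-target trial several titration choices are left to the provider or investigator, so institutions could differ in mean HbA1c change. A two-sample test leaves any such difference in the error term. If the arms are also unevenly spread over institutions, the difference enters the treatment estimate.

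The same holds for the stratum and for baseline HbA1c, which can run from 9% to 15% at entry. A stratification factor chosen at design would normally appear in the analysis, but here it enters only if variable selection keeps it. A non-inferiority claim also needs one decision rule set before the data are seen. A series of tests followed by a data-driven model offers several treatment estimates that could be set against 0.4%. At stake are some precision and a clear basis for the conclusion.

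**Working it through.** **Inputs from Sample Size Calculation:** SD of change 0.85, margin 0.4, true difference 0, one-sided alpha 0.05, 57 per group, 20% attrition, 75 recruited per group.

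**Assumption:** two equal-sized institutions whose mean HbA1c change differs by d, with total SD kept at 0.85. The documents give no site variance, so a range of d is shown.

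1. **The plan's own figure.** Normal approximation: n = 2 × 0.85² × (1.645 + 0.842)² / 0.4² = 55.8, so 56. With the exact non-central t, 56 per group gives 79.7% power and 57 gives 80.3%. The stated 57 reproduces. After 20% loss, 75 × 0.8 = 60 per group remain, with 82.1% power.

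2. **Implied interval.** One-sided 0.05 corresponds to a two-sided 90% interval. Its half-width is t(0.95, 2n − 2) × 0.85 × √(2/n), which is 0.264 at n = 57 and 0.257 at n = 60.

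3. **Effect of an institution term on width.** Share of variance R² = (d²/4) / 0.85². The width is multiplied by √(1 − R²).
   - d = 0: R² = 0 and there is no gain. Losing one degree of freedom widens the interval by 0.01%, and losing two by 0.02%.
   - d = 0.1: R² = 0.3%, interval 0.2% narrower.
   - d = 0.2: R² = 1.4%, 0.7% narrower.
   - d = 0.3: R² = 0.0225/0.7225 = 3.1%, 1.6% narrower.
   - d = 0.5: R² = 0.0625/0.7225 = 8.7%, 4.4% narrower.

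4. **Power at 60 per group, with arms balanced within institution.** With the term it is 83.1% (d = 0.3) and 85.0% (d = 0.5). The unadjusted test in the same setting has 82.5% and 83.2%. The gain is 0.6 and 1.8 percentage points.

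5. **Error rate of the unadjusted test if arms are balanced within institution.** Residual SD = √(0.85² − d²/4) = 0.837 (d = 0.3) or 0.812 (d = 0.5). Real one-sided error = Φ(−1.645 × 0.85 / residual SD) = 4.7% or 4.3%, instead of 5%.

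6. **If balance within institution is not forced.** The unadjusted test keeps its 5% error on average over randomisations. In a single trial the estimate shifts by d times the difference between arms in the share of patients from one institution. That shift has SD d × √(2 × 0.25/60) = 0.091d, or about 0.03 points (d = 0.3) and 0.05 points (d = 0.5). An institution term removes it.

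7. **Baseline HbA1c and stratum.** The documents do not say how much of the change these explain. If they explained an assumed 20 to 30%, the half-width at 57 per group would fall from 0.264 to between 0.236 and 0.221 (about 11 to 16%), and power would rise from 80.3% to between 87% and 91%.

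**The case against.** The strongest reply is that the plan excludes nothing. A reader might infer that the primary analysis is the unadjusted test alone. The text does not support that, because a final model follows and institution or the stratum could enter it. This stands as a limit on the point: the terms are unspecified, not ruled out. It does not answer the point, since terms chosen from the data cannot serve as a pre-specified non-inferiority analysis.

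A reader might also infer that randomisation was stratified by institution. The documents refer to a single table and declare one factor, HbA1c. Mailing that table to each institution does not establish balance within it. The 4.7% and 4.3% error rates are therefore conditional on a design the text does not state.

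A third tempting reading is that offsets between several laboratories contaminate the outcome. Assessments for Efficacy names the clinical laboratory of "Grady Memorial Hospital and Emory University, a NGSP-certified laboratory. Subjects will" is worded in the singular and can be read as one laboratory or two. A constant offset cancels in a patient's change if the same laboratory runs both samples, and nothing suggests that patients switch. That the plan does not require the same laboratory is a missing detail, not evidence of bias.

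Finally, the size is assumed and modest, and the sample size already meets its target without adjustment. That stands.

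**Conclusion.** The point holds as a low-cost improvement. The deciding analysis of the primary outcome is not pre-specified, and neither institution nor the declared HbA1c stratum is assured a place in it.

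For the institution term, the interval narrows by about 1.6 to 4.4% under assumed differences of 0.3 to 0.5 points between two equal institutions, worth 0.6 to 1.8 points of power like for like. There is no gain if institutions are alike. Baseline HbA1c and the stratum may well matter more, though their contribution is also assumed.

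The documents do not support reading this as a threat to validity or as a shortage of power. The unadjusted test is conservative if arms are balanced within institution and holds its level on average if they are not. The stated 57 per group reproduces without any covariate.

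**What to change.** In Statistical Methods, replace the variable-selection step for the primary outcome with one pre-specified linear model of week-26 HbA1c change. It should contain treatment, baseline HbA1c, the randomisation stratum (below 10 versus 10 or above) and institution as a fixed factor. State that non-inferiority is judged from this model's treatment difference against 0.4%, using the upper limit of the two-sided 90% interval that the stated one-sided 0.05 implies. The two-sample tests can stay as supporting analyses. Say in advance whether Emory Midtown and Grady count as one institution or two.

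One optional sentence in Assessments for Efficacy could require each patient's screening and week-26 HbA1c to be run in the same laboratory.

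The cost is a short text change and about one degree of freedom per extra institution. No new data, patients or procedures are needed, and the sample size stays as it is.
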